#### 13.1.4 Response Criteria RECIST 1.1

##### 13.1.4.1 Evaluation of Target Lesions

Complete Response (CR): Disappearance of all target lesions. Any pathological lymph nodes (whether target or non-target) must have reduction in short axis to <10 mm (<1 cm).

Partial Response (PR): At least a 30% decrease in the sum of the diameters of target lesions, taking as reference the baseline sum diameters.

Progressive Disease (PD): At least a 20% increase in the sum of the diameters of target lesions, taking as reference the smallest sum on study (this includes the baseline sum if that is the smallest on study). In addition to the relative increase of 20%, the sum must also demonstrate an absolute increase of at least 5 mm (0.5 cm). (Note: the appearance of one or more new lesions is also considered progressions).

Note: Modified iRECIST is also being used in that given that immunotherapy is being administered in this protocol, patients may remain on study at first progression if investigator feels the patient is deriving clinical benefit. However, if in subsequent scans, the lesions continue to progress beyond previous scan, the patient will be considered to have progressive disease and should be taken off protocol. Any question should be discussed with the sponsor.

Stable Disease (SD): Neither sufficient shrinkage to qualify for PR nor sufficient increase to qualify for PD, taking as reference the smallest sum diameters while on

study.

#### 13.1.4.2 Evaluation of Non-Target Lesions

**Complete Response (CR):** Disappearance of all non-target lesions and normalization of tumor marker level. All lymph nodes must be non-pathological in size (<10 mm [<1 cm] short axis).

Note: If tumor markers are initially above the upper normal limit, they must normalize for a patient to be considered in complete clinical response.

**Non-CR/Non-PD:** Persistence of one or more non-target lesion(s) and/or maintenance of tumor marker level above the normal limits.

**Progressive Disease (PD):** Appearance of one or more new lesions and/or *unequivocal progression* of existing non-target lesions. *Unequivocal progression* should not normally trump target lesion status. It must be representative of overall disease status change, not a single lesion increase.

Although a clear progression of “non-target” lesions only is exceptional, the opinion of the treating physician should prevail in such circumstances, and the progression status should be confirmed at a later time by the review panel (or Principal Investigator). The same note about PD under target lesions also applies here.

#### 13.1.4.3 Evaluation of Best Overall Response

The best overall response is the best response recorded from the start of the treatment until disease progression/recurrence (taking as reference for progressive disease the smallest measurements recorded since the treatment started). The patient's best response assignment will depend on the achievement of both measurement and confirmation criteria.

#### For Patients with Measurable Disease (*i.e.*, Target Disease)

Target Lesions	Non-Target Lesions	New Lesions	Overall Response	Best Overall Response when Confirmation is Required*
CR	CR	No	CR	≥4 wks. Confirmation**
CR	Non-CR/Non-PD	No	PR	≥4 wks. Confirmation**
CR	Not evaluated	No	PR	
PR	Non-CR/Non-PD/not evaluated	No	PR	
SD	Non-CR/Non-PD/not evaluated	No	SD	Documented at least once ≥4 wks. from baseline**

PD	Any	Yes or No	PD	no prior SD, PR or CR
Any	PD***	Yes or No	PD	
Any	Any	Yes	PD	

\* See RECIST 1.1 manuscript for further details on what is evidence of a new lesion.

\*\* Only for non-randomized trials with response as primary endpoint.

\*\*\* In exceptional circumstances, unequivocal progression in non-target lesions may be accepted as disease progression.

Note: Patients with a global deterioration of health status requiring discontinuation of treatment without objective evidence of disease progression at that time should be reported as “*symptomatic deterioration.*” Every effort should be made to document the objective progression even after discontinuation of treatment.

iRECIST Note: Given that immunotherapy is being given in this protocol, patients may remain on study at first progression if investigator feels the patient is deriving clinical benefit. However, if in subsequent scans, the lesions continue to progress beyond previous scan, the patient will be considered to have progressive disease and should be taken off protocol. Any question should be discussed with the sponsor.

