### 7.6.3 On Treatment Imaging

Patients will undergo imaging (CT of affected target areas- ideally CT with contrast unless contraindication; MRI also acceptable) every 12 weeks +/- 5 days. If patient has a PR or CR, confirmation scans are required at 4 weeks after scan in which response was first observed.

The specific method of imaging to use (CT, CT with contrast, MRI) may change per the subject's clinical needs, and this determination for which imaging method to use will rely on the treating investigator's clinical discretion.

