### 10.4 Randomization:

Patients will be randomized into arms 1 and 2 using R (R Core Team. 2012) at time of registration (if screening labs are to be obtained on same day as treatment randomization may be performed at the time all other eligibility criteria are informally confirmed to allow adequate time for treatment planning). The UC Project Manager will work with the statistician to ensure each patient is assigned to one of the arms correctly. Randomization of patients does not affect the primary or secondary endpoints of this study as response and safety is based on the combination treatment in which both groups will receive. The patients are randomized for the exploratory endpoints in order to better understand the difference of effects of metformin versus pembrolizumab on the immune system.

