### 13.1 Antitumor Effect – Solid Tumors

For the purposes of this study, patients should be re-evaluated for response every 9 weeks. In addition to a baseline scan, confirmatory scans should also be obtained 4 weeks following initial documentation of objective response.

Response and progression will be evaluated in this study using the international criteria proposed by the revised Response Evaluation Criteria in Solid Tumors (RECIST) guideline (version 1.1) [Eur J Ca 45:228-247, 2009]. However, iRECIST will also be used if pseudoprogression is suspected. Changes in the largest diameter (unidimensional measurement) of the tumor lesions and the shortest diameter in the case of malignant lymph nodes are used in the RECIST criteria.

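### A footnote to the best-overall-response table, read literally, switches off response confirmation in this randomized trial, against the text of section 13.1.4.3, and the 6/19 rule does not say which responses count

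*Combined protocol and SAP*

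**What the plan says.** - **Section 13.1.4.3, table for patients with measurable disease.** The confirmation entries for CR and PR (4 weeks or later) and the minimum interval for SD carry a double-asterisk footnote: "Only for non-randomized trials with response as primary endpoint".
- **Section 13.1.4.3, text above the table.** "The patient's best response assignment will depend on the achievement of both measurement and confirmation criteria".
- **Section 10.4.** "Patients will be randomized into arms 1 and 2 using R". The same section adds: "Randomization of patients does not affect the primary or secondary endpoints of this study". The reason given is that both arms receive the combination; the randomization serves the exploratory immune endpoints.
- **Section 7.6.3.** "If patient has a PR or CR, confirmation scans are required at 4 weeks after scan in which response was first observed".
- **Section 13.1** (and, in nearly the same terms, the opening of section 13). "confirmatory scans should also be obtained 4 weeks following initial documentation of objective response".
- **Sections 10.1 and 10.2.** The primary endpoint is overall response by RECIST 1.1 and iRECIST. The study is called successful if 6 of 19 evaluable patients respond. Neither section says whether a response must be confirmed.

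**The concern.** The footnote sets two conditions: the trial is non-randomized, and response is its primary endpoint. This trial meets the second and, taken at its word, fails the first. An analyst who follows the table would then count a PR or CR seen on one scan. An analyst who follows the sentence above the table would not. Both instructions sit in the subsection that derives the primary endpoint, and the statistical section does not choose between them.

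The go decision is a bare count in a small pooled group with no concurrent control for response. Shrinkage that is transient, or that reflects measurement error, can add responders under the single-scan reading, and nothing in the design offsets them. Which reading applies should be fixed before the responses are tabulated.

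**Working it through.** **1. The passages side by side.**

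| Place | What it implies for a PR or CR seen once |
|---|---|
| 13.1.4.3, footnote, with 10.4 (randomized) | Counts; confirmation does not apply |
| 13.1.4.3, text | Does not count; confirmation is part of the assignment |
| 7.6.3, 13, 13.1 | A confirming scan is called for; silent on how to count a response that is not confirmed |
| 10.1, 10.2 | Silent |

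The direct contradiction is between the footnote and the text of 13.1.4.3. It needs no numerical assumption.

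**2. A constructed patient on whom the readings differ.** Target sums are 60 mm at baseline, 41 mm at the first scan and 47 mm at the confirming scan, with no new lesions.
- First scan: 41/60 − 1 = −31.7%, which meets the 30% decrease for PR.
- Confirming scan: 47/60 − 1 = −21.7% from baseline, so PR is not met. 47/41 − 1 = +14.6% from the nadir, below the 20% needed for PD in 13.1.4.1.

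By the footnote the patient is a responder. By the text the PR is unconfirmed and the patient is not.

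**3. The plan's own figures.** From section 10.2: target ORR 32%, 25 enrolled, 19 evaluable, success at 6/19, and ORR of 15–20% for pembrolizumab alone.
- Margin of error, 1.96 × √(0.32 × 0.68 / n): 18.3 points at n = 25 and 21.0 at n = 19. This reproduces the stated value of close to 20%.
- 6/19 = 31.6%, in line with the 32% target. One patient is 1/19 = 5.3 points.

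**4. The 6/19 rule if only confirmed responses count.** Exact binomial P(X ≥ 6 | 19, p): 5.4% at p = 0.15, 11.1% at 0.18, 16.3% at 0.20.

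**5. The rule if single-scan responses also count.** The documents give neither a measurement error nor a non-confirmation rate, so a share u of non-responders counted on one scan is assumed. The counted rate becomes p + u(1 − p).

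The range for u comes from a simulation with two on-study scans and an assumed reading error:
- Low case, 10% error and no true change: PR in 1.1% unconfirmed against 0.1% confirmed, a gap of about 1%.
- High case, 15% error and true changes spread by 15% around zero: 13.3% against 5.6%, a gap of about 8%.

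| True ORR p | P(≥6/19), confirmed only | u = 1%: counted rate, P(≥6/19) | u = 8%: counted rate, P(≥6/19) |
|---|---|---|---|
| 15% | 5.4% | 15.85%, 6.7% | 21.8%, 21.8% |
| 18% | 11.1% | 18.82%, 13.1% | 24.56%, 31.6% |
| 20% | 16.3% | 20.8%, 18.7% | 26.4%, 38.6% |

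**6. A second route.** Assume instead that a fraction f of first responses fails confirmation, so the counted rate is p/(1 − f). For f = 10%, 20% and 30%, P(≥6/19) is 8.2%, 12.9% and 20.6% at a confirmed ORR of 15%, and 23.2%, 33.2% and 47.1% at 20%. The direction is the same; the size depends on an f that the documents do not supply.

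**The case against.** The strongest reply is that the documents already show what is meant. The text of 13.1.4.3 demands confirmation, and sections 7.6.3, 13 and 13.1 call for the scan. Section 10.4 says that randomization has no bearing on the primary endpoint, so for response the study works as one pooled group with response as primary endpoint. That is the setting in which the footnote itself wants confirmation. The footnote speaks of trials in general and looks like template wording. This stands as a reading of intent, and it limits the point to a repair of wording. It does not remove the point: the table that assigns the primary outcome still carries a condition that gives the wrong answer here, and the success rule is silent.

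The reply also rightly limits three stronger readings that a reader might infer.
- **That the plan means to count single-scan responses.** The weight of the text is against this.
- **That the footnote contradicts 7.6.3.** That section requires the scan but does not say how an unconfirmed response is counted. The direct clash is inside 13.1.4.3.
- **That the footnote raises the chance of a false go to 32% or 39%.** Those are the top ends of an assumed range. They need 15% error on every reading and true changes centred on zero. The simulation has no net growth and no progression, whereas growing tumours seldom show a spurious 30% decrease and best response is recorded only until progression. At the low end, and at the plan's own 15% reference rate, the rise is from 5.4% to 6.7%.

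**Conclusion.** The inconsistency is real and rests on the text alone: in a trial that randomizes, the literal footnote removes the confirmation that the same subsection requires, and neither 10.1 nor 10.2 says that ORR or 6/19 counts confirmed responses. Confirmation is evidently intended, so the derivation should be made to say so.

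The firm number is 5.3 points of ORR for each patient whose classification changes. The effect on the go rule is illustrative. For u between 1% and 8%, the chance of meeting 6/19 rises by 1.3 to 16.4 points at a true ORR of 15%, by 2.0 to 20.5 points at 18%, and by 2.4 to 22.3 points at 20%. The upper ends are pessimistic. The documents do not support a claim that the trial will in fact be inflated by this amount.

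**What to change.** - **13.1.4.3, footnote.** Replace it with a statement that the confirmation requirement and the SD minimum interval apply to this study, because both arms are pooled for response.
- **10.1 and 10.2.** State that ORR and the 6/19 rule count confirmed CR and PR only.
- **Unconfirmed responses.** State that an evaluable patient whose CR or PR is not confirmed stays in the denominator as a non-responder. This covers PD at the confirming scan and the absence of a second scan. Best response is then assigned by the RECIST 1.1 confirmation rules.
- **7.6.3.** As a secondary point, align its timing (at 4 weeks) with the table's criterion (4 weeks or later), so that a scan taken slightly early does not fail confirmation on a technicality.

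The cost is a few sentences. No extra scans are needed, since 7.6.3 already requires the confirming scan. The reported ORR may be slightly lower than under a single-scan count.

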#### For Patients with Non-Measurable Disease (i.e., Non-Target Disease)

Non-Target Lesions	New Lesions	Overall Response
CR	No	CR
Non-CR/non-PD	No	Non-CR/non-PD*
Not all evaluated	No	not evaluated
Unequivocal PD	Yes or No	PD
Any	Yes	PD

* ‘Non-CR/non-PD’ is preferred over ‘stable disease’ for non-target disease since SD is increasingly used as an endpoint for assessment of efficacy in some trials so to assign this category when no lesions can be measured is not advised
		

#### 13.1.5 Duration of Response

Duration of overall response: The duration of overall response is measured from the time measurement criteria are met for CR or PR (whichever is first recorded) until the first date that recurrent or progressive disease is objectively documented (taking as reference for progressive disease the smallest measurements recorded since the treatment started).

The duration of overall CR is measured from the time measurement criteria are first met for CR until the first date that progressive disease is objectively documented.

Duration of stable disease: Stable disease is measured from the start of the treatment until the criteria for progression are met, taking as reference the smallest measurements recorded since the treatment started, including the baseline measurements.

### 13.1.6 Progression-Free Survival

PFS is defined as the duration of time from start of treatment to time of progression or death, whichever occurs first.

### 13.1.7 Overall Survival

OS is defined as the duration of time a patient is alive from start of treatment until time of death.

## **STUDY OVERSIGHT AND DATA REPORTING / REGULATORY REQUIREMENTS**

### **14.1 Study Oversight**

This protocol is monitored at several levels, as described in this section. The UC Principal Investigator is responsible for monitoring the conduct and progress of the clinical trial, including the ongoing review of accrual, patient-specific clinical and laboratory data, and routine and serious adverse events reporting. The UC Principal Investigator has access to the data at all times through REDCap. All Study Investigators at participating sites who register/enroll patients to this study are responsible for timely submission of data via REDCap and timely reporting of adverse events to the UC PI and in REDCap.

### **14.2 SMART IRB**

The UC HRPP will utilize the Streamlined, Multisite, Accelerated Resources for Trials IRB Reliance platform (SMART IRB) master IRB reliance agreement to establish reliance arrangements with the research sites participating in this study.

Launched in 2016, SMART IRB is currently funded by the NIH Clinical and Translational Science Awards (CTSA) Program, grant number UL1TR002541-01S1. The platform serves as a roadmap for institutions to implement The National Institutes of Health (NIH) Policy on the Use of a Single Institutional Review Board for Multisite Research.

The UC IRB will act as the IRB of record for this protocol and will perform initial review and have continuing oversight of the protocol and research sites in accordance with the human subjects protection requirements of its FWA, the FWAs of relying IRBs, the federal regulations, and ethical principles referenced therein.

### **14.3 Data Reporting**

Data collection and storage will be managed by the University of Cincinnati Cancer Center, Clinical Trials Office (UCCC CTO). The UCCC CTO will maintain storage of all clinical data in accordance with federal guidelines and GCP. Data will be entered in a secure, password protected storage databases REDCap and the UC CTMS (clinical trial management system). All hardcopies of data will be securely maintained (in a locked room or cabinet) and will only be accessible to

members of the study team or UCCC CTO personnel.

#### 14.3.1 Data and Safety Monitoring

Any new significant finding that may affect the patient's willingness to continue in this study will be shared with patients. Immediately after the study is approved and before the first patient is enrolled, investigators will meet, develop and finalize all measurements/variables for the study. Each patient, once enrolled, will be provided a unique ID for the study. Personal information, such as name, SSN, address, phone number and DOB, will be de-identified. Confidentiality will be maintained during the phases of the trial including monitoring, preparation of interim results, review, and response to monitoring recommendations.

Exceptions may be made under circumstances where there are serious adverse events or when it is deemed appropriate for patient safety.

Study progress will be monitored regularly by the UCCC Data Safety Monitoring Board (DSMB). DSMB membership consists of persons independent of, and without any conflicts of interest with, this trial. The DSMB includes experts in the fields of relevant clinical expertise (oncology) and biostatistics.

It is the responsibility of the UC Investigator to ensure that the DSMB is apprised of all new safety information relevant to the study. Study progress & safety information will be prepared by the DSMB Coordinator with input from the UC PI as to the current status of the trial. This compiled information presented to the DSMB will include: a narrative summary from the UC PI as to trial progress and identification of any trends of significance or explanation of any SAEs or other safety related events; the accrual rate with projected completion date for the accrual phase; exclusion rates and reasons; pretreatment characteristics of patients accrued when relevant; and, the frequency and severity of adverse events.

The DSMB will function in an advisory capacity and recommendations/requests from the DSMB will be reviewed by the UC investigator and promptly addressed.

The study data from participating sub-sites will be reviewed remotely via REDCap and in person by the UCCC Study Monitor as per the Clinical Monitoring Plan (on file with UCCC CTO office).

## APPENDIX A PERFORMANCE STATUS CRITERIA

ECOG Performance Status Scale		Karnofsky Performance Scale	
Grade	Descriptions	Percent	Description
0	Normal activity. Fully active, able to carry on all pre-disease performance without restriction.	100	Normal, no complaints, no evidence of disease.
		90	Able to carry on normal activity; minor signs or symptoms of disease.
1	Symptoms, but ambulatory. Restricted in physically strenuous activity, but ambulatory and able to carry out work of a light or sedentary nature (e.g., light housework, office work).	80	Normal activity with effort; some signs or symptoms of disease.
		70	Cares for self, unable to carry on normal activity or to do active work.
2	In bed <50% of the time. Ambulatory and capable of all self-care, but unable to carry out any work activities. Up and about more than 50% of waking hours.	60	Requires occasional assistance, but is able to care for most of his/her needs.
		50	Requires considerable assistance and frequent medical care.
3	In bed >50% of the time. Capable of only limited self-care, confined to bed or chair more than 50% of waking hours.	40	Disabled, requires special care and assistance.
		30	Severely disabled, hospitalization indicated. Death not imminent.
4	100% bedridden. Completely disabled. Cannot carry on any self-care. Totally confined to bed or chair.	20	Very sick, hospitalization indicated. Death not imminent.
		10	Moribund, fatal processes progressing rapidly.
5	Dead.	0	Dead.

## APPENDIX B FORMULA TO ESTIMATE RENAL FUNCTION USING SERUM CREATININE

Formulas to estimate renal function using serum creatinine provided by the NCI's Investigational Drug Steering Committee (IDSC) Pharmacological Task Force in table below.

1. Estimated glomerular filtration rate (eGFR) using the Chronic Kidney Disease Epidemiology Collaboration (CKD-EPI) (Levey *et al.*, 2009).

Formulae:

Race and Sex	Serum Creatinine (SCr), $\mu\text{mol/L}$ (mg/dL)	Equation
Black	Female $\leq 62$ ( $\leq 0.7$ )	$\text{GFR} = 166 \times (\text{SCr}/0.7)^{-0.329} \times (0.993)^{\text{Age}}$
	Female $> 62$ ( $> 0.7$ )	$\text{GFR} = 166 \times (\text{SCr}/0.7)^{-1.209} \times (0.993)^{\text{Age}}$
	Male $\leq 80$ ( $\leq 0.9$ )	$\text{GFR} = 163 \times (\text{SCr}/0.9)^{-0.411} \times (0.993)^{\text{Age}}$
	Male $> 80$ ( $> 0.9$ )	$\text{GFR} = 163 \times (\text{SCr}/0.9)^{-1.209} \times (0.993)^{\text{Age}}$
White or other	Female $\leq 62$ ( $\leq 0.7$ )	$\text{GFR} = 144 \times (\text{SCr}/0.7)^{-0.329} \times (0.993)^{\text{Age}}$
	Female $> 62$ ( $> 0.7$ )	$\text{GFR} = 144 \times (\text{SCr}/0.7)^{-1.209} \times (0.993)^{\text{Age}}$
	Male $\leq 80$ ( $\leq 0.9$ )	$\text{GFR} = 141 \times (\text{SCr}/0.9)^{-0.411} \times (0.993)^{\text{Age}}$
	Male $> 80$ ( $> 0.9$ )	$\text{GFR} = 141 \times (\text{SCr}/0.9)^{-1.209} \times (0.993)^{\text{Age}}$

SCr in mg/dL; Output is in mL/min/1.73 m^2 and needs no further conversions.

---

2. eGFR using the Modification of Diet in Renal Disease (MDRD) Study (Levey *et al.*, 2006).

$175 \times \text{SCr}^{-1.154} \times \text{age}^{-0.203} \times 0.742$  (if female)  $\times 1.212$  (if black)

Output is in mL/min/1.73 m^2 and needs no further conversions.

---

3. Estimated creatinine clearance (CLcr) by the Cockcroft-Gault (C-G) equation (Cockcroft and Gault, 1976).

$$\text{CLcr (mL/min)} = \frac{[140 - \text{age (years)}] \times \text{weight (kg)}}{72 \times \text{serum creatinine (mg / dL)}} \{ \times 0.85 \text{ for female patients} \}$$

Followed by conversion to a value normalized to 1.73 m^2 with the patient's body surface area (BSA).

